On the day of study drug administration (V1a), subjects will be randomized (2:1:2:1); URG101:placebo:lidocaine:heparin) and will receive a single administration of one of four intravesical treatments in a blinded fashion, based on random assignment:

1. Combination product, URG101 (buffered heparin-lidocaine)
2. Placebo: [REDACTED]
3. Lidocaine: [REDACTED]
4. Heparin: [REDACTED]

Subjects will be monitored for 2 hours in the clinic after study drug administration.

CLINICAL PROTOCOL SYNOPSIS (continued)

	
Subjects will maintain a urination log and symptom diary after discharge and will return to the clinic the following day to complete the in-clinic study procedures and collection of the study diary.
 
The following will be completed according to the schedule of assessments over a 24-hour period after study drug administration: the 11-point NRS for bladder pain and urgency; the PORIS questionnaire; vital signs assessments; blood samples for safety laboratory assessments, i.e. blood coagulation (prothrombin time [INR] and activated partial thromboplastin time [aPTT]), and plasma lidocaine concentrations; adverse events; and concomitant medication assessments.
 
Subjects will be contacted within 48 to 72 hours after the last study treatment to follow-up on any ongoing adverse events after the last clinic visit.
 
The clinical study will plan to randomize 180 subjects. After 90 (50%) subjects have been enrolled and treated, the IDMC will examine the conditional power and determine if a modification to the sample size is required to yield an overall power of 90%. An adjustment to the type 1 error rate will not be necessary if the conditional power is >39% at the interim assessment.
 
The IDMC will consist of 3 members: 1 physician expert in IC/BPS, 1 expert in clinical development, and a biostatistician. None of the IDMC members will be associated with study personnel; all communication between the IDMC and study personnel will be pre-defined and governed by the IDMC charter. The IDMC will have access to unblinded pain scores to perform their ranking of the pain endpoints and for assessment of conditional power.

Estimated Number of Subjects:	A target of 180 subjects subject to adjustment by the IDMC. A maximum of 300 subjects will be enrolled in Study URG101-105.
Number of Study Sites:	Up to 30 sites in the United States and Canada

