9.1.3 Home Assessment

After instructions, the subjects will be discharged from the clinic and reminded to

return the next day for the optional 24 hour Follow-up Visit. However, return of subject diaries including 24 hour assessments are mandatory. All assessments and their respective timing are provided in Table 4. The following assessments will occur >2 hours post study drug administration but before 24-hour Follow-up Visit (V2):

- 11-point NRS for bladder pain and urgency at 4 hours (\pm 30 minutes), 6 hours (\pm 30 minutes), 8 hours (\pm 30 minutes), 10 hours (\pm 30 minutes), and 12 hours (\pm 30 minutes) (only during times the subject is awake);
- the PORIS questionnaire at 12 hours after study drug administration or before the subject goes to bed for the evening;
- urination log;
- adverse event reporting;
- and concomitant medications.

9.1.4 24-Hour Follow-up Visit (Visit 2; Optional)

Approximately 24 hours after study drug administration, the subjects will return to the clinic for end-of-study assessments. The following assessments will occur:

- subject's diary collection is mandatory to evaluate the efficacy of URG101;
- 11-point NRS for bladder pain and urgency at 24 hours (\pm 2 hours) is mandatory to be completed and returned;
- the PORIS questionnaire at 24 hours (\pm 2 hours) after study drug administration is mandatory to be completed and returned;
- vital signs measurements at 24 hours (\pm 2 hours) after study drug administration (i.e., systolic and diastolic blood pressure, heart rate, respiratory rate, and oral body temperature) is optional;
- and recording of any adverse events or concomitant medications is mandatory to be collected and returned for safety evaluation.

In the opinion of the Investigator, if the subject appears responsible to perform the 24 hour assessments, correctly fill out the diary for all of the at home assessments, and the Investigator and the subject have made acceptable arrangements for the return of the diaries, answering of any follow up questions, and for the subject's treatment and care after 24 hours, then Visit 2 may be considered an optional protocol visit to the clinic.

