9.1.5 End-of Study Follow-up

The site staff will call each subject within 48 to 72 hours of study drug administration to check on subject status and to ascertain AE and concomitant medication status.

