9.5.1.10.3 Adverse Events and Other Events of Interest

An AE is any untoward medical occurrence in a subject who is administered an investigational product. An AE does not necessarily have a causal relationship with the study drug.

The criteria for identifying AEs include the following:

- Any unfavorable and unintended sign (including an abnormal laboratory finding), symptom, or disease temporally associated with the use of an investigational product, whether or not considered related to the investigational product
- Any new disease or exacerbation of an existing disease
- Any deterioration in non-protocol-required measurements of a laboratory value or other clinical test (e.g., electrocardiogram [ECG] or x-ray) that results in symptoms, a change in treatment, or discontinuation of study drug
- Recurrence of an intermittent medical condition (e.g., headache) not present pretreatment (baseline)
- An abnormal laboratory test result should be considered an AE if the identified laboratory abnormality leads to any type of intervention, whether prescribed in the protocol or not, and after repeat confirmatory testing has been conducted

A laboratory result should be considered by the investigator to be an AE if it includes the following:

- Results in an intervention, based on medical evaluation (e.g., potassium supplement for hypokalemia)

- Results in any out of range laboratory value that in the investigator's judgment fulfills the definitions of an AE with regard to the subject's medical profile

All AEs observed during the study will be reported on the CRF. All AEs, regardless of relationship to study drug or procedure, should be collected beginning from the time the subject signs the ICF through the last visit. AEs reported prior to randomization will be termed medical history. SAEs will not be considered medical history and will be collected for 72 hours after the last dose.

Abnormal laboratory values should not be listed as separate AEs if the values are considered to be part of the clinical syndrome that is being reported as an AE. Any laboratory abnormality considered to constitute an AE should be reported as an AE on the CRF.

It is the responsibility of the investigator to review all laboratory findings in all subjects and determine if they constitute an AE. Medical and scientific judgment should be exercised in deciding whether an isolated laboratory abnormality should be classified as an AE.

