9.5.6 Reporting of Serious Adverse Events, Pregnancy, and Other Events of Interest

9.5.6.1 Reporting of Serious Adverse Events

All SAEs, regardless of their relationship to study drug, must be reported on a completed SAE form by email or fax as soon as possible to [REDACTED] but should be reported no later than 24 hours from the time the investigator becomes aware of the SAE.

Any death or any life-threatening event should be reported immediately by telephone to [REDACTED] The immediate report should be followed up within 1 business day by emailing or faxing the completed SAE form.

SAEs, regardless of causality assessment, must be collected through the last visit and up to 72 hours after drug administration. All SAEs must be followed to resolution or, if resolution is unlikely, to stabilization. Any SAE judged by the investigator to be related to the study treatment should be reported to the sponsor regardless of the length of time that has passed since study completion.

For urgent safety issues, please ensure all appropriate medical care is administered to the subject, and contact the appropriate study team member listed in the Investigator Study File.

It is very important that the SAE form be filled out as completely as possible at the time of the initial report. This includes the investigator's assessment of causality.

Any follow-up information received about SAEs should be forwarded within 1 business day of its receipt. If the follow-up information changes the investigator's assessment of causality, this should also be noted on the follow-up SAE form.

Preliminary SAE reports should be followed as soon as possible by detailed descriptions of additional information including copies of hospital case reports, autopsy reports, and other documents, if requested by the sponsor.

The investigator must notify the IRB of the occurrence of the SAE, in writing, if required by their institution. A copy of this communication must be forwarded to the sponsor or the contract research organization to be filed in the sponsor's Trial Master File.

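### After about 24 hours the protocol has no single end time for adverse-event collection, and a compliant closing call can leave up to 24 of the 72 SAE hours without contact

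*Combined protocol and SAP*

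**What the plan says.** - **Section 9.5.1.10.3, AEs.** AEs, whatever their relationship to treatment, "should be collected beginning from the time the subject signs the ICF through the last visit". The sentence before is broader: "All AEs observed during the study will be reported on the CRF".
- **SAEs.** The same paragraph of 9.5.1.10.3 adds: "SAEs will not be considered medical history and will be collected for 72 hours after the last dose". Section 9.5.6.1 repeats the limit: "SAEs, regardless of causality assessment, must be collected through the last visit and up to 72 hours after drug administration".
- **Sections 9.1.3 and 9.1.4.** AE reporting is one of the home assessments between 2 hours and Visit 2, and the AE record due at 24 hours must be collected and returned. If the investigator judges the subject reliable and arrangements for the diary are in place, "then Visit 2 may be considered an optional protocol visit to the clinic".
- **Section 9.1.5.** "The site staff will call each subject within 48 to 72 hours of study drug administration", with the purpose of establishing AE and concomitant-medication status.
- **Synopsis, Study Design.** The call has the same timing but a narrower purpose: "to follow-up on any ongoing adverse events after the last clinic visit".
- **Section 9.7.1.8.** Concomitant medications are counted to 72 hours after the dose.
- **Section 9.7.1.11.** A treatment-emergent AE (TEAE) is one that arises during treatment. No end time is given, and only TEAEs enter the summary tables.

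**The concern.** Safety and tolerability is a stated objective (8.2) and AEs are a safety endpoint (9.7.1.3). The percentages of subjects with a TEAE should therefore rest on one observation window that every site applies in the same way. The protocol ties the end of AE collection to a last visit that it does not define and that need not be the same contact for every subject. It then sets other end points for SAEs, for the closing call and for concomitant medications.

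Two things are at stake. Compliant sites, of about 30 planned, could treat the same late non-serious event differently. And an SAE that occurs after an early closing call would reach the site only if the subject or someone else volunteered it.

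**Working it through.** The plan states no figure to reproduce. The check sets the windows side by side, in hours after dosing, and subtracts.

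**Inputs**
- Visit 2 and the 24-hour records: 24 h ± 2 h, that is 22 to 26 h (9.1.4).
- SAE window: to 72 h (9.5.1.10.3, 9.5.6.1).
- Closing call: at any time t from 48 to 72 h (9.1.5, synopsis).
- Concomitant medications: to 72 h (9.7.1.8).

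**Step 1: coverage to 24 hours.** Home AE reporting runs from 2 hours to Visit 2, and return of the 24-hour AE record is compulsory whether or not the subject comes to the clinic. Every subject is therefore covered to about 24 h.

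**Step 2: AE end against SAE end.** If the last visit is Visit 2, the nominal AE end is about 24 h, and the two windows differ by 72 − 24 = 48 h (46 to 50 h over the visit window).

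**Step 3: a new non-serious AE that starts at 30 h**

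| Rule | Is the event captured? |
|---|---|
| 9.5.1.10.3, collection to the last visit | No: 30 h is later than 22 to 26 h |
| 9.5.1.10.3, all AEs observed during the study | Arguably yes: the end of the study is not defined there |
| 9.1.5, call to establish AE status | Yes |
| Synopsis, call for ongoing AEs | No: it was not ongoing at the last visit |
| 9.7.1.8, a drug taken to treat it | Drug recorded: 30 h is before 72 h |
| 9.7.1.11, TEAE definition | Undetermined: no end time after a single dose |

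The rules give different answers, and the analysis section does not settle them.

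**Step 4: part of the SAE window after the closing call.** Gap = 72 − t.
- t = 48 h: 72 − 48 = 24 h, and 24/72 = 33% of the SAE window.
- t = 60 h: 72 − 60 = 12 h, and 12/72 = 17%.
- t = 72 h: 0 h.

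All three call times comply with 9.1.5, so the stretch without scheduled contact ranges from 0 to 24 h.

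**The case against.** The strongest reply is that the operational sections already do the work. A reader might infer from 9.5.1.10.3 that, for a subject who skips Visit 2, AE collection ends when the clinic stay ends, since the synopsis says "Subjects will be monitored for 2 hours in the clinic after study drug administration". The documents do not support that. Section 9.1.3 schedules AE reporting at home, and 9.1.4, the section that makes the visit optional, also makes the 24-hour AE record compulsory. Section 9.5.2.3 adds telephone contact to confirm return of the diary and answer questions, and 9.1.5 has every subject called. This part of the reply stands in full.

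A reader might also infer that the AE rates have no common denominator. That goes too far. The denominator is the safety analysis set (9.7.1.5), and incidence is the percentage of subjects with at least one event (9.7.1.11). What can differ is how long, and how actively, events are sought after 24 hours.

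Three further points have some force:
- The limit to ongoing events appears only in the synopsis. Section 9.1.5 has no such limit and asks about AEs and medications together, so a call that uncovers a drug taken at 30 h should uncover the event too. This shows which reading is probably intended, but it does not remove the conflict with the collection rule in 9.5.1.10.3.
- The duty to collect SAEs to 72 hours does not depend on the call, and 9.5.6.1 requires SAEs judged related to be reported however late. The 24-hour gap is thus a maximum, and a gap in scheduled contact rather than in obligation. Even so, a site cannot report what it has not heard about.
- A longer window for SAEs than for AEs can be a deliberate choice. If so, the AE end still needs a stated time.

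The content of Table 4 is missing from the text available. It may show which contacts collect AEs.

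**Conclusion.** The point holds for the period after about 24 hours. The end of AE collection is undefined, it conflicts with the closing call in 9.1.5, and the synopsis and 9.1.5 disagree on what the call is for. New non-serious events after the 24-hour record can be handled differently by compliant sites, and up to 24 of the 72 SAE hours (33%) can pass without scheduled contact.

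The weight is minor to moderate. A reader might take this as a source of bias between arms, but the trial is double-blind and nothing in the documents links the Visit 2 waiver or the time of the call to treatment. The issue is uneven ascertainment, not a demonstrated loss of safety data. The conclusion assumes that Table 4 does not already set one window. The actual size of the SAE gap depends on when sites call, which the documents leave open between 48 and 72 hours.

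**What to change.** 1. In the synopsis, 9.5.1.10.3 and 9.5.6.1, state one window for all subjects: AEs and SAEs, new or ongoing, are collected from consent through 72 hours after study drug administration, whether or not Visit 2 is attended.
2. In 9.7.1.11, give the TEAE definition the same 72-hour end, so that the summary tables match what is collected. The concomitant-medication window in 9.7.1.8 already ends there.
3. In 9.1.5 and the synopsis, make the existing call no earlier than 72 hours (for example 72 to 96 hours) and have it ask about new and ongoing events.
4. Check Table 4 against the result.

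This is a cheap improvement: wording, plus a later time for a call already planned, with no added visit. The drawbacks are recall about a day longer (72 − 48 = 24 h at the early end of the call window) and a few more non-serious AEs to record.

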9.5.1.6 Catheter Tolerance

All subjects will be catheterized with the hydrophilic ColoplastSpeediCath 8 Fr and 12 Fr, respectively (for females and males). Each subject will be assessed for the ability to tolerate the catheter after randomization into the study, based on the

investigator's judgment.

9.5.1.7 [REDACTED]

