Every effort must be made by the investigator to categorize each AE according to its severity and its relationship to the study treatment.

Assessing Severity of Adverse Events:

AEs will be graded on a 3-point scale (mild, moderate, severe) and reported in the detail indicated on the CRF. The definitions are as follows:

Mild	Discomfort noticed, but no disruption of normal daily activity
Moderate	Discomfort sufficient to reduce or affect normal daily activity
Severe	Incapacitating, with inability to work or to perform normal daily activity

The criteria for assessing severity are different than those used for seriousness (see Section [9.5.1.10.3](#), Serious Adverse Events and Other Events of Interest for the definition of an SAE).

The causal relationship of the study drug to an AE will be assessed as related or unrelated, as follows:

Assessing Causality of Adverse Events:

Table 3. Assessment of Causality of AEs

Term	Definition
Definitely related	The AE is clearly related to the investigational agent(s) or research intervention: the AE has a temporal relationship to the administration of the investigational agent(s) or research intervention and follows a known pattern of response, and no alternative cause is present.
Probably related	The AE is likely related to the investigational agent(s) or intervention: the AE has a temporal relationship to the administration of the investigational agent(s) or research intervention and follows a known or suspected pattern of response, but an alternative cause may be present.
Possibly related	The AE may be related to the investigational agent(s) or intervention: the AE has a temporal relationship to the administration of the investigational agent(s) or research intervention and follows a suspected pattern of response, but an alternative cause is present.
Unrelated (or Not Related)	The AE is clearly not related to the investigational agent(s) or intervention: the AE has no temporal relationship to the administration of the investigational agent(s) or research intervention, and follows no known or suspected pattern of response, and an alternative cause is present.

AE = adverse event.

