9.7.1.11 Adverse Events

The AE verbatim descriptions (investigator terms from the CRF) will be classified into standardized medical terminology using the Medical Dictionary for Regulatory Activities (MedDRA). Adverse events will be coded to the MedDRA lower level term closest to the verbatim term. The linked MedDRA preferred term and primary system organ class (SOC) are also captured in the database.

A TEAE is defined as an AE that emerges during treatment, having been absent at baseline and:

- Reemerges during treatment, having been present before treatment (baseline) but stopped before treatment,

or

- Worsens in severity during treatment relative to the pretreatment state, when the AE is continuous.

Adverse events will be summarized and listed for the safety analysis set. Only those AEs that are treatment-emergent will be included in summary tables. Summary tables will be by treatment group and overall. The incidence (%) will be determined by calculating the number of subjects with at least 1 event and the percentage of subjects with TEAEs by SOC and by preferred term. All AEs, treatment emergent or otherwise, will be presented in subject data listings.

The incidence of TEAEs will be reported as the number (percentage) of subjects with TEAEs by SOC and preferred term. A subject will be counted only once within a SOC and preferred term, even if the subject experiences more than one TEAE within a specific SOC and preferred term. The number (percentage) of subjects with TEAEs will also be summarized by maximum severity (mild, moderate, or severe).

The number (percentage) of subjects with TEAEs will also be summarized by relationship to study drug (possibly related, probably related, and not related).

The number (percentage) of subjects with treatment-related TEAEs will be summarized by SOC and preferred term. Treatment-related TEAEs include those AEs considered by the investigator to be possibly or probably related to study treatment. The number (percentage) of subjects with treatment-related TEAEs will also be summarized by maximum severity (mild, moderate, or severe).

A subject data listing of all AEs leading to death will be provided. Additionally, a subject data listing of all AEs leading to discontinuation from study drug will be provided.

The number (percentage) of subjects with SAEs will be summarized by MedDRA SOC and preferred term for each treatment group. A subject data listing of all SAEs will be provided.

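### Table 3 grades causality against the drug or the research intervention, but section 9.7.1.11 reports that grade as relationship to study drug, so catheter-caused events can enter the relatedness tables in every arm

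*Combined protocol and SAP*

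**What the plan says.** The sentence introducing Table 3 in section 9.5.1.10.3 confines the judgement to the drug: "The causal relationship of the study drug to an AE will be assessed as related or unrelated, as follows". The definitions beneath it do not. The Definitely related row judges the event by its relationship "to the investigational agent(s) or research intervention: the AE has a temporal relationship to the administration of the investigational agent(s) or research intervention". The Probably, Possibly and Unrelated rows carry the same alternative, in places shortened to *or intervention*. The documents do not define research intervention.

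The Unrelated grade has three conditions that must all hold. The first is that "the AE has no temporal relationship to the administration of the investigational agent(s) or research intervention". The others are that no known or suspected response pattern is followed and that an alternative cause is present.

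Section 9.7.1.11 says that TEAEs will be "summarized by relationship to study drug (possibly related, probably related, and not related"), and adds: "Treatment-related TEAEs include those AEs considered by the investigator to be possibly or probably related to study treatment". Neither sentence mentions Definitely related. The same section plans a table that ignores causality: "The incidence of TEAEs will be reported as the number (percentage) of subjects with TEAEs by SOC and preferred term". Summary tables are by treatment group.

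Section 9.5.1.6 states: "All subjects will be catheterized with the hydrophilic" catheter, in one size for women and another for men. Section 9.4.1 has all four treatments given through a urethral catheter. Section 9.5.1.10.3 mentions drug and procedure as distinct possible sources when it says which events to collect, but describes only one causality grade.

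**The concern.** The grade that investigators are told to assign and the label that the tables put on it do not refer to the same thing. Instillation by catheter can itself cause urethral or bladder symptoms, and every subject has that exposure, placebo included. If research intervention is taken to cover catheterization, an event due to the catheter alone satisfies the timing and pattern conditions for a related grade, and section 9.7.1.11 then presents it as related to study drug.

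Two things are at stake. The relatedness tables would overstate drug-related events in every arm. A background common to all arms would also pull the arms together in those tables. Safety and tolerability is a stated objective (section 8.2), and these tables are pre-specified. The definitions are to be applied at about 30 sites, so the conflict between the lead-in and the table also invites different sites to grade the same event differently.

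**Working it through.** The plan states no adverse-event rate, test or power, so there is no figure to reproduce. The check is first a trace through the text, then an illustration on assumed rates.

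**Trace.** Take urethral pain soon after instillation that the investigator attributes to the catheter.

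1. *Table 3 read literally, with catheterization as a research intervention.* The timing condition is met and the pattern is known or suspected. With no alternative cause, the grade is Definitely related. If the underlying bladder disease may be, or is, an alternative cause, the grade is Probably or Possibly related. Unrelated is unavailable because of the timing.
2. *Where it goes in section 9.7.1.11.* Probably and Possibly are counted as treatment-related. Definitely has no category in the relationship summary and is outside the treatment-related definition.
3. *Lead-in read as governing, so drug only.* The catheter becomes the alternative cause. The event is still close in time to the drug, so it still fails the first condition for Unrelated. Possibly related remains open if a drug pattern is suspected. Deleting the intervention wording alone therefore does not solve the problem.

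**Illustration (all rates assumed).** Let d1 and d0 be the drug-caused rates on URG101 and placebo, and c the catheter-caused rate in every arm, independent of drug effects. If every catheter event is counted as related, the related-event rate in an arm is 1 − (1 − c)(1 − d). The difference between arms is then (1 − c)(d1 − d0).

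With d1 = 5% and d0 = 1%:

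| c | URG101 | Placebo | Difference (points) | Ratio |
|---|---|---|---|---|
| 0 | 5.0% | 1.0% | 4.0 | 5.00 |
| 10% | 14.5% | 10.9% | 3.6 | 1.33 |
| 20% | 24.0% | 20.8% | 3.2 | 1.15 |
| 30% | 33.5% | 30.7% | 2.8 | 1.09 |

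For example, at c = 10%: 1 − 0.90 × 0.95 = 0.145 and 1 − 0.90 × 0.99 = 0.109.

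With d1 = 15% and d0 = 0, and 60 v 30 subjects as in the Synopsis, exact two-sided Fisher power at 0.05 is:

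| c | URG101 | Placebo | Difference (points) | Power |
|---|---|---|---|---|
| 0 | 15.0% | 0% | 15.0 | 0.70 |
| 5% | 19.3% | 5% | 14.3 | 0.37 |
| 10% | 23.5% | 10% | 13.5 | 0.28 |
| 20% | 32.0% | 20% | 12.0 | 0.19 |
| 30% | 40.5% | 30% | 10.5 | 0.13 |

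Between c = 0 and c = 30%, power falls from 0.25 to 0.08 for d1 = 10%, and from 0.93 to 0.21 for d1 = 20%. Section 9.7.1.9 plans descriptive safety statistics only, so power here only gauges the blurring. The rows with c = 0 assume that investigators separate the two sources perfectly.

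**The case against.** A reader might infer that catheter events will count as drug-related and so hide a drug signal. The documents do not support that, for three reasons.

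- All TEAEs are tabulated by treatment group whatever their causality grade, and the placebo arm is catheterized in the same way. The randomized comparison in that table already separates drug from procedure. Section 9.7.1.3 names adverse events, not related events, as the safety endpoint.
- Counting is possible, not certain. Research intervention is undefined, and the lead-in points to the drug. An investigator who follows the lead-in would not call catheter trauma drug-related on the strength of this phrase.
- A clear catheter event with no other cause would be Definitely related, and would fall outside the treatment-related definition instead of swelling it.

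These points stand and limit the consequence to the relatedness tables. They do not rescue those tables. The last one shows a second fault: the strongest grade is missing from both summaries.

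It is also fair to say that the catheter rates are invented. Section 9.3.2 excludes subjects with significant urethral discomfort on catheterization, which may lower them. In the first illustration the absolute difference shrinks far less than the ratio does.

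Finally, the CRF and the separate SAP promised in section 9.7 are not available here, so a procedure field may exist. It would not by itself correct the Table 3 definitions or the section 9.7.1.11 summaries.

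**Conclusion.** The text is wrong as written and should be corrected. Table 3 grades against drug or intervention, while its lead-in and section 9.7.1.11 call the result relationship to study drug. Catheter-caused events can therefore be reported as drug-related in every arm, which inflates the relatedness tables and blurs the contrast between arms in them. The Unrelated definition adds to this by ruling itself out for anything near instillation. The omission of Definitely related works the other way, dropping the most confidently attributed events.

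The effect is confined to attribution. No efficacy conclusion changes, and the all-causality TEAE comparison stands. The size cannot be estimated from the documents. On the assumed rates, the difference between arms keeps its sign and loses the fraction c, that is 5 to 30% over the range shown, while the ratio falls much more. Those figures also assume that all catheter events are counted as related and that the sources are independent. If some are graded Unrelated or Definitely related, the dilution is smaller.

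**What to change.** 1. In Table 3, remove both *or research intervention* and *or intervention* from all four definitions, so that the grade refers to study drug only, as the lead-in says. Removing only the longer phrase would leave the shorter one in three of the four rows.
2. Restate Unrelated so that a more likely alternative cause, such as catheterization, can suffice despite closeness in time.
3. Add to the adverse-event CRF a separate, non-exclusive item for relationship to catheterization or study procedure, if it is not already there.
4. In section 9.7.1.11, base the relationship and treatment-related tables on the study-drug grade, include Definitely related in both, and tabulate procedure-related events separately by arm. Keep the all-causality TEAE table as the main comparison between arms.

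The cost is a wording change and one extra field per event. The real limitation is that blinded investigators may not always be able to tell catheter effects from instillate effects, and could attribute true drug irritation to the catheter. That is why the procedure item should be non-exclusive and the all-causality table should keep its place.
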